2.2.1 Subgroup of interest

The primary efficacy endpoint, progression free survival (PFS), overall response rate (ORR) and clinical benefit rate (CBR) will be summarized for the following subgroups. The subgroup analyses will be based on the mFAS:

- **Demography**
 - Age ≥ 65 vs age < 65 years
 - Gender (if more than 10 in men)
 - Ethnicity (white vs Asian vs black vs. other)
- **Prior Medication History**
 - Line of advanced anti-cancer treatment in any setting (1st line vs. 2nd line)
 - Prior chemotherapy use (adjuvant vs neoadjuvant vs. no prior use)
 - Patient population based on endocrine status and line of therapy:
 - a. relapsed with documented evidence of progression more than 12 months from completion of (neo)adjuvant endocrine therapy and then subsequently progressed with documented evidence of progression while on or after only one line of endocrine therapy for metastatic disease (yes vs. no)

b. relapsed with documented evidence of progression while on (neo) adjuvant endocrine therapy or within 12 months from completion of (neo)adjuvant endocrine therapy with no treatment for metastatic disease (yes vs. no)

- **Disease Characteristics**

- Number of metastatic sites (<3 vs. >=3)
- Visceral disease (Yes vs. No)
- Bone lesions only (Yes vs. No)
- PTEN loss of expression (Loss of expression vs. No loss of expression)

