The primary analysis from the phase III [CBYL719C2301 (SOLAR-1)] study confirms statistically significant and clinically relevant benefit with alpelisib in combination with fulvestrant in PIK3CA mutant, HR+ HER2- advanced breast cancer patients who have progressed on AI treatment. The BYLieve study was originally designed to investigate the benefit risk ratio of PIK3CA inhibitor treatment following prior use of CDK4/6 inhibitor treatments but was restricted to patients who received CDK4/6 inhibitors as their last treatment prior to study entry. Since then, the approval of CDK4/6 inhibitors for use in first line metastatic breast cancer has led to increasing number of patients receiving the treatment in an earlier line, followed by systemic chemotherapy or ET. Based on these developments in the current treatment landscape for aBC and the results from SOLAR -1 study, the enrollment into BYLieve study is being extended to patients who may have received systemic chemotherapy or an ET as immediate prior treatment and have previously failed AI treatment (either in adjuvant or metastatic setting).

The sample size from cohorts A and B was revised to allow for a more robust assessment of benefits vs. risk in the investigated patient populations.

Rationale to allow assessment of random blood glucose levels (non-fasted):

The primary analysis of SOLAR-1 [CBYL719C2301] confirms previously established safety and tolerability for alpelisib from early phase studies. The class effect of hyperglycemia can be monitored through regular blood tests and upon occurrence, is readily manageable through existing guidelines recommended in the protocol. Based on this information, the study is being amended to allow for monitoring of either fasting or random blood glucose (RBG) levels (non-

fasted). Patients who experience rise in fasting or RBG levels will be subjected to previous management guidelines: plasma glucose levels can be monitored via peripheral blood tests at the discretion of the investigator.

Rationale to add the interim analysis

A second interim analysis will be performed when approximately patients (50% of enrolled patients) have been treated in the study (regardless of cohort) a have at least 6 months of follow up. This interim analysis will be performed to report preliminary efficacy (ORR, CBR) as well as key safety data in a descriptive fashion to provide additional information in this patient population.

Changes to the protocol

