Cohort A: Patients who received any CDK 4/6 inhibitor plus any AI as immediate prior treatment will receive alpelisib + fulvestrant

Cohort B: Patients who received any CDK 4/6 inhibitor plus fulvestrant as immediate prior treatment will receive alpelisib + letrozole

Cohort C: Patients who received systemic chemotherapy or ET (as monotherapy or in combination with targeted treatment except CDK 4/6i + AI) as immediate prior treatment will receive alpelisib + fulvestrant.

Note: In Cohort C, ET includes letrozole, fulvestrant and CDK 4/6 inhibitor plus fulvestrant.

[figure not shown]
The study includes two phases:

Core Phase: includes treatment phase for all patients from FPFT until 18 months post LPFT + 1 month Safety follow-up (total 19 months post LPFT)

Extension Phase: includes treatment phase starting at the end of the treatment Core Phase until LPLV (up to 36 months). The extension treatment phase is only for patients who are continuing to benefit from study treatment at the end of the Core Phase who are not eligible for PSDS in their country based on local regulations. Patients will continue on their existing study treatment assigned in the Core Phase until discontinuation (refer to Section 7.1.5) or LPLT of the Extension Phase. Note: If PSDS becomes available for a patient or a rollover protocol becomes available, the patient should be discontinued from the study and access treatment via PSDS or rollover trial (whichever occurs first).

Patients who are benefiting from the study treatment and are eligible for PSDS will exit the trial at the end of the Core Phase.

Figure 4-2 Study Design

A Steering Committee (SC) will be established comprising investigators and Novartis representatives participating in the trial to ensure transparent management of the study according to the protocol through recommending and approving modifications as outlined in Section 8.7.

Treatment crossover between cohorts will not be permitted in this study.

This study will use an Interactive Response Technology (IRT) system for patient molecular screening, screening, enrollment, discontinuation, and study medication management.

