 - **Note**: For women using therapy-induced amenorrhea other than ovarian radiation, goserelin or leuprolide, serial measurements (per local guidelines) of FSH and/or estradiol are needed to ensure menopausal status.
 - b. Patient is premenopausal defined as either:
 - Patient had last menstrual period within the last 12 months OR
 - If on tamoxifen or toremifene with in the past 14 days, plasma estradiol and FSH must be in the premenopausal range per local normal range, OR
 - In case of therapy induced amenorrhea, plasma estradiol and/or FSH must be in the premenopausal range per local normal range
 - **Note:** Throughout this document, peri-menopausal and pre-menopausal status is grouped together and referred as "Premenopausal"
- 7. Patients must have documented evidence of tumor progression on or after
 - CDK 4/6 inhibitor treatment as last treatment regimen in cohorts A and B
 - AI treatment (either in adjuvant or metastatic setting) and received systemic chemotherapy or ET (monotherapy or combination except CDK 4/6i + AI) as last treatment regimen in cohort C: Note, upon completion of enrollment of Cohort B,

- No more than two (2) prior anti-cancer therapies for aBC. Each unique regimen or 'line' is defined as a single or combination of medications given for a new relapse/ recurrence. Maintenance therapies, where applicable, must be regarded as part of the main treatment.
- Received no more than one prior regimen of chemotherapy for the treatment of advanced/metastatic disease is permitted,
 - Note: Patients who received chemotherapy in (neo) adjuvant therapy for breast cancer are eligible.
- Recovered to grade 1 or better from any adverse events (except alopecia or other toxicities not considered a safety risk for the patient at investigator's discretion) related to previous anti-cancer therapy prior to study entry,
- 8. Patients must have either:

Measurable disease, i.e. at least one measurable lesion as per RECIST v1.1 criteria. (Tumor lesions previously irradiated or subjected to other locoregional therapy will only be considered measurable if disease progression at the treated site after completion of therapy is clearly documented),

or

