Patients who are benefiting from treatment and are eligible for PSDS will exit the trial at the end of the Core Phase. At the start of the Core Phase, patients will be assigned to a cohort based on previous therapy (AI or fulvestrant) as indicated below:

[figure not shown]
Cohort A: Patients who received any CDK 4/6 inhibitor plus any AI as immediate prior treatment will receive alpelisib + fulvestrant

Cohort B: Patients who received any CDK 4/6 inhibitor plus fulvestrant as immediate prior treatment will receive alpelisib + letrozole

Cohort C: Patients who received systemic chemotherapy or ET (as monotherapy or in combination with targeted treatment except CDK 4/6i + AI) as immediate prior treatment will receive alpelisib + fulvestrant

Note: In Cohort C, ET includes letrozole, fulvestrant and CDK4/6 inhibitor plus fulvestrant.

Figure 1-1 **Study Design**

Treatment crossover between cohorts will not be permitted in this study.

The primary objective of the study is to assess the proportion of patients who are alive without disease progression at 6 months based on local investigator assessment per RECIST v1.1 separately in Cohorts A and C (alpelisib in combination with fulvestrant) and Cohort B (alpelisib in combination with letrozole) among patients with HR+, HER2-negative aBC harboring a PIK3CA mutation who have progressed on or after prior treatments.

The primary analysis for each cohort will be performed 6 months after the last patient enrolled in that specific cohort has started treatment. The final analysis will be performed after LPLV of the study which include cumulative data (eg safety and clinical benefit) since the start of Core Phase for the patients who enter the Extension Phase.

Prior to the final analysis, cohort specific analyses maybe performed when all patients included in the corresponding cohort have approximately 18 months of follow-up.

Three Interim Analyses (IA) are planned for this study. The first IA will be performed after at least **CC1** patients receiving alpelisib plus fulvestrant (cohort A) have at least 6 months of follow up. The second IA will be performed when approximately **CC1** patients (50% enrolled patients) have been treated in the study (regardless of cohort) and have at least 6 months of follow-up. The third IA will be performed after the Core Phase has ended.

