2.4.2 Prior, concomitant and post therapies

Prior anti-cancer therapy

The number and percentage of patients who received any prior anti-neoplastic medications, prior anti-neoplastic radiotherapy or prior anti-neoplastic surgery will be summarized by cohort. Prior anti-neoplastic medications will be summarized by therapy type (e.g. chemotherapy, hormonal therapy etc.), setting (e.g. adjuvant, metastatic, etc.) and also by lowest ATC class, preferred term and treatment. Summaries will include total number of regimens, best response and time from last treatment to progression for the last therapy.

The medication therapy type of any combination therapy will be classified based on the following order: chemotherapy, biologic therapy, targeted therapy, hormonal therapy. For example, a combination therapy of chemotherapy and hormonal therapy will be classified as 'chemotherapy'. For radiotherapy, locations and setting of last therapy will be summarized. For prior surgery, time since last surgery, procedure and residual disease of last therapy will be summarized.

In addition, number (%) of patients who received any hormonal therapy (irrespective of given in combination with chemotherapy or biologic or targeted therapy), any aromatase inhibitors, any hormonal therapy other than aromatase inhibitors in any setting and in the metastatic setting, any prior CDK4/6 inhibitors will be summarized by cohort.

Separate listings will be produced for prior anti-neoplastic medications, radiotherapy, and surgery.

Anti-neoplastic medications will be coded using the WHO Drug Dictionary (WHO-DD); anti-neoplastic surgery will be coded using MedDRA. Details regarding MedDRA and WHO-DD version will be included in the footnote in the tables/listings.

The above analyses will be performed using the FAS .

Post treatment anti-cancer therapy

Anti-neoplastic therapies since discontinuation of study treatment will be listed and summarized by ATC class, preferred term, by cohort by means of frequency counts and percentages using FAS.

Concomitant medications

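### The prior-chemotherapy subgroup has no level for patients whose only chemotherapy was for advanced disease, and its adjuvant and neoadjuvant levels overlap

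*SAP*

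**What the plan says.** SAP 2.2.1 (Amendment 4, the version to which the extension-phase SAP refers for all main analyses) lists this factor under prior medication history: "Prior chemotherapy use (adjuvant vs neoadjuvant vs. no prior use"). The factor applies to four endpoints: the primary endpoint, PFS, ORR and CBR. On the population it states: "The subgroup analyses will be based on the mFAS".

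The entry criteria admit a wider range of chemotherapy histories. Protocol 5.2, criterion 7, reads: "Received no more than one prior regimen of chemotherapy for the treatment of advanced/metastatic disease is permitted". A note beneath it adds: "Patients who received chemotherapy in (neo) adjuvant therapy for breast cancer are eligible". Neither statement is limited to one cohort.

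Protocol 4.1 describes Cohort C as "Patients who received systemic chemotherapy or ET (as monotherapy or in combination with targeted treatment except CDK 4/6i + AI) as immediate prior treatment", and SAP 1.1 repeats the definition. The protocol's rationale for adding Cohort C (Amendment 3) speaks of CDK4/6 inhibitors moving into first-line metastatic use, with more patients "receiving the treatment in an earlier line, followed by systemic chemotherapy or ET".

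SAP 2.4.2 tabulates prior anti-neoplastic medication by therapy type and by "setting (e.g. adjuvant, metastatic, etc".), using the FAS.

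**The concern.** A subgroup factor should place every patient in exactly one level. This one names two early-disease settings and a level for no use, in a trial of advanced disease that expressly admits patients who had chemotherapy for that disease. The programmer would have to choose, without a rule, between leaving such patients out, counting them under *no prior use* (which is untrue as worded), or putting them in a (neo)adjuvant level where they do not belong.

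The study is single-arm within each cohort, so these summaries are one of the few planned ways to see whether results hold across treatment histories. As written, the table cannot show outcomes after chemotherapy for advanced disease. Depending on the choice made, the *no prior use* row could mix chemotherapy-naive patients with patients who had just come off chemotherapy.

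**Working it through.** **1. The plan's own figure, to fix what is not at issue.** Inputs: 112 patients per cohort and success at 44 or more (Protocol 10.4.2, SAP 2.5.2); null rate 0.30 (Protocol summary, data analysis); true rate 0.45 and one-sided 2.5% (Protocol 10.8, SAP 3.1).

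- Exact alpha: P(X ≥ 44 | n = 112, p = 0.30) = 0.0225.
- Exact power: P(X ≥ 44 | n = 112, p = 0.45) = 0.9055.
- Clopper-Pearson lower 95% limit: 30.2% at 44/112 and 29.4% at 43/112, so 44 is the correct cut-off.

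The stated design reproduces. No prior-chemotherapy variable enters it.

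**2. Eligible histories against the SAP levels.** Write A for adjuvant, N for neoadjuvant and M for advanced/metastatic chemotherapy. Criterion 7 and its note permit every combination of the three (M limited to one regimen), which gives 2 × 2 × 2 = 8 histories.

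| History | SAP 2.2.1 level | Proposed level |
|---|---|---|
| None | no prior use | none |
| A | adjuvant | (neo)adjuvant only |
| N | neoadjuvant | (neo)adjuvant only |
| A + N | two levels | (neo)adjuvant only |
| M | no level | advanced |
| A + M | adjuvant, M hidden | advanced |
| N + M | neoadjuvant, M hidden | advanced |
| A + N + M | two levels, M hidden | advanced |

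Under the SAP levels, 3 of the 8 histories are placed once and fully described. One has no level, two fit two levels, and two fit one level that hides the advanced-setting exposure (3 + 1 + 2 + 2 = 8). Under the proposed levels each history falls in exactly one (1 + 3 + 4 = 8).

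**3. Who can have history M.** In Cohorts A and B the last regimen contains a CDK4/6 inhibitor, but criterion 7 allows two prior therapies for advanced disease, one of which may be chemotherapy. In Cohort C chemotherapy may itself be the last regimen. The cohort definition does not state the setting of that chemotherapy; that it was given for advanced disease is an inference from the Amendment 3 rationale. The exclusion list for the per-protocol set in SAP 2.2 itself mentions chemotherapy in the metastatic setting, so the SAP recognises such patients elsewhere.

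**4. Whether another provision repairs the gap.**

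- The line-of-treatment subgroup in SAP 2.2.1 counts lines and does not separate chemotherapy from endocrine therapy.
- The endocrine-status subgroups there are defined by relapse timing and number of lines, not by chemotherapy.
- SAP 2.4.2 describes prior therapy by type and setting on the FAS, without efficacy results.
- The missing category in SAP 2.1 is for absent data; here the exposure is known.

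**5. Scale.** The documents give no count. For one cohort at its planned size, if a share s had chemotherapy only for advanced disease, the number with no level is 112 × s: 11 at 10%, 28 at 25% and 56 at 50%. These shares are assumptions that show scale only. The gap in the levels does not depend on them.

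**The case against.** The strongest reply is that very little rests on this table. SAP 2.2.1 only summarises endpoints by subgroup, and the study is non-comparative. No reference level, contrast, interaction test or model is specified for this factor. The subgroup by line of advanced treatment covers the same four endpoints and captures some of the prior-treatment burden, and SAP 2.4.2 will show how many patients had chemotherapy in each setting. Patients who cannot be placed might be shown in a missing category rather than silently merged. *No prior use* could also be read as no (neo)adjuvant use, which would make the list exhaustive. The A + N overlap needs only a precedence rule.

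Most of this limits the size of the point and does not remove it. The two neighbouring provisions do not give efficacy after advanced-setting chemotherapy. A missing category would be visible but would mislabel a known exposure. The alternative reading of *no prior use* is not stated, and it would put patients treated for advanced disease in the same row as patients who never had chemotherapy.

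The objection does defeat some stronger readings:

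- A reader might infer that the omitted group defines Cohort C. Chemotherapy is one of two routes, the other being endocrine therapy, and its share is not given. Cohorts A and B are also exposed.
- A reader might infer that a reference group is contaminated. The SAP names no reference group, and no text directs these patients to *no prior use*.
- A reader might assume that 20% to 40% of Cohort C had chemotherapy for advanced disease and count 22 to 45 patients without a level (0.20 × 112 = 22.4; 0.40 × 112 = 44.8). The percentages have no source in the documents. The count would also include patients with A + M or N + M, who do fit a level.

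**Conclusion.** The point holds as a defect in a stated classification. It affects one factor and four endpoints; tabulated by cohort, that is 4 × 3 = 12 descriptive summaries. Those summaries would omit or misplace patients treated with chemotherapy only for advanced disease. They would also place patients with both adjuvant and neoadjuvant chemotherapy ambiguously and hide later exposure in patients treated in both early and advanced settings.

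A reader might go on to doubt the primary result. The documents do not support that: the 44-of-112 rule, its alpha of 0.0225 and its power of 0.9055, and the cohort-level estimates of PFS, ORR and CBR, do not use this variable.

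The conclusion rests on the wording of SAP 2.2.1 and criterion 7. It needs no assumption about how many patients are affected, which the documents leave unknown.

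**What to change.** Replace the levels in SAP 2.2.1 with: prior chemotherapy for advanced/metastatic disease (with or without (neo)adjuvant chemotherapy); (neo)adjuvant chemotherapy only; none. Report them within each cohort, with the number of patients in each level.

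The levels can be derived from the therapy type and setting already collected for SAP 2.4.2. That section also classifies any combination containing chemotherapy as chemotherapy, so no new data or coding rule is needed.

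The cost is one SAP line and a small re-tabulation. The adjuvant versus neoadjuvant split is lost as an efficacy subgroup but can stay in the baseline description. Enrolment was complete by 14-Dec-2020, each primary analysis was set six months after the cohort's last patient started, and SAP Amendment 4 is dated 24-Mar-2022, so some outputs probably already exist. For any cohort where they do, the revised table should be labelled a post hoc change in the CSR.

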2.3 Patient disposition, demographics and other baseline characteristics

The FAS will be used for all baseline and demographic summaries.

Basic demographic and background data

All demographic and baseline disease characteristics data will be summarized and listed by cohort. Categorical data (e.g. gender, age groups: <65 and \geq 65 years, race, ethnicity, Child bearing status, ECOG performance status) will be summarized by frequency counts and percentages; the number and percentage of patients with missing data will be provided. Continuous data (e.g. age, weight, height, body mass index) will be summarized by descriptive statistics (N, mean, median, standard deviation, Q1, Q3, minimum and maximum). BMI (kg/m^2) will be calculated as weight[kg] / (height[m] 2) using weight and height at Baseline.

Diagnosis and extent of cancer

Summary statistics will be tabulated for diagnosis and extent of cancer. This analysis will include the following: primary site of cancer, details of tumor histology/cytology, histological grade, stage at initial diagnosis, time since initial diagnosis, time from initial diagnosis to first recurrence/progression (in months), time since most recent relapse/progression to start of treatment (in months), stage at time of study entry, presence/absence of target and non-target lesions, number and type of metastatic sites involved, HER2 receptor status, estrogen receptor (ER) status, progesterone receptor (PgR) status and hormone receptor (ER and/or PgR) status.

Note: Presence/absence of target and non-target lesions will be based on the data collected on RECIST target/non-target lesion assessment eCRF pages. Metastatic sites will be based on diagnosis page.

Medical history and ongoing conditions

Medical history and ongoing conditions, including cancer-related conditions and symptoms entered on (e) CRF will be summarized and listed by cohort. Separate summaries will be presented for ongoing and historical medical conditions. The summaries will be presented by primary system organ class (SOC), preferred term (PT) and cohort. Medical history and current medical conditions will be coded using the Medical Dictionary for Regulatory Activities (MedDRA) terminology. The MedDRA version used for reporting will be specified in the CSR and as a footnote in the applicable tables/listings.

Other

All data collected at baseline will be listed.

